Secondary Endpoints	
 
Best objective response on the trial (by IMWG criteria).
 
Progression-free survival.
 
Negative MRD (≤10^-5, by clonoSEQ®), including imaging plus MRD-negativity (≤10^-5 in bone marrow and no area of PET-CT FDG uptake greater than mediastinal blood pool or surrounding normal tissue).
 
Duration of response on maintenance.
 
Time to progression/relapse after CAR-T.
 
Overall survival for the entire study population.
 
Adverse events on the trial.
 
QoL parameters.
 
					
Exploratory Objectives	Exploratory: BCMA expression by flow cytometry and soluble     BCMA/BAFF/APRIL levels will be monitored at screening/baseline, and     after two, six, and 12 cycles.					
Exploratory Endpoints	Baseline and on-treatment sBCMA/BAFF/APRIL and BCMA expression on myeloma cells.					
Study Design	This is a multicenter phase II, open-label study evaluating the efficacy and safety of belantamab mafodotin maintenance in participants with RRMM who have received commercially available anti-BCMA CAR-T-cell therapy.  Subjects will be enrolled 60–120 days after CAR-T and receive belantamab mafodotin as maintenance therapy. Although screening can occur as early as day 60 post CAR-T therapy, study treatment cannot be started prior to day 90 post CAR-T therapy. Each maintenance cycle will have a duration of 56 days (+/- three days) and belantamab mafodotin will be administered at a dose of 1.9 mg/kg IV on day 1 of each cycle. The study will enroll up to 45 subjects with an interim analysis performed when 23 patients have been treated and followed to the 12th month after					

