- 16. NGS for MRD assessment (clonoSEQ®) will be performed on bone marrow aspirate sample. Bone marrow aspiration with MRD assay (first pull, in subjects found to be MRD-informative based on clone identification sample) and flow cytometry/cytotoxicity assays will be performed within seven days before cycle 3 day 1, and cycle 7 day 1 and within seven days before or after cycle 12 day 56. Samples are also to be obtained/sent for correlative studies (refer to Appendix 5).
- 17. Patient-reported outcomes (refer to Appendix) PRO assessments should be completed before any other study procedures are performed (except for blood draws).:
  - a. EORTC-QLQ-MY20 and EORTC QLQ-C30
    - i. Collect at cycle 1 day 1 (prior to treatment), cycle 3 day 1, cycle 7 day 1, cycle 9 day 1, and 70-day safety visit.
  - b. OCULAR SURFACE DISEASE INDEX (OSDI)
    - i. Collect at cycle 1 day 1 (prior to treatment), every cycle day 1, and 70-day safety visit.
- 18. For patients who discontinue treatment prior to progression, continue standard-of-care follow-up every three months until progression or start of another treatment (whichever comes first), then continue to long-term follow-up.
- 19. Long-term survival data collected/reported approximately every six months (+/- 30 days).
- 20. Urine dipstick for protein may be used to assess for presence of urine protein. Albumin/creatinine ratio needs to be done in any participant with urine dipstick result of ≥1+ at screening, or with positive protein if urine dipstick protein quantification is not available.

Short Title: MCW EMBRACE TRIAL 15 Version No.: 3
Version Date: 12/29/2022

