#### **5.2.3 Dose Modification Related Corneal Adverse Reactions**

All belantamab mafodotin dose modifications and stopping criteria are to be based on the Keratopathy Visual Acuity (KVA) Scale for Treatment-related Corneal Toxicities. Corneal events will be graded according to this scale. Refer to reporting section for additional requirements.

Table 4. Corneal adverse reactions and recommendations for belamantab mafodotin dosing.

Grade per KVA scale	Grade 1	Grade 2	Grade 3	Grade 4
*Recommended Dosage Modifications	Continue treatment at current dose.	Withhold belantamab mafodotin until improvement in both corneal examination findings and changes in BCVA to grade 1 or better and resume at current dose.	Withhold belantamab mafodotin until improvement in both corneal examination findings and changes in BCVA to grade 1 or better and resume at reduced dose.  If already on lowest dose, participant continues treatment at same dose.	Consider permanent discontinuation of belantamab mafodotin.  If based on benefit risk assessment and treatment of belantamab mafodotin is being considered, withhold treatment until improvement in both corneal examination findings and change in BCVA to grade 1 or better and resume at reduced dose.  If already on lowest dose, participant continues treatment at same dose.

Table 5: Keratopathy Visual Acuity (KVA) Scale for treatment-related corneal toxicities

Grade per KV	VA scale	Grade 1	Grade 2	Grade 3	Grade 4
	Corneal examination finding(s)	Mild superficial keratopathy a	Moderate superficial keratopathy b	Severe superficial keratopathy c	Corneal epithelial defect d
Corneal Toxicities	Change in BCVA e	Decline from baseline of one line on Snellen Visual Acuity	Decline from baseline of two or three lines (and Snellen Visual Acuity not worse than 20/200)	Decline from baseline by more than three lines (and Snellen Visual Acuity not worse than 20/200)	Snellen Visual Acuity worse than 20/200

Abbreviations: BCVA=Best-Corrected Visual Acuity; KVA=Keratopathy Visual Acuity.

Dose reductions of belantamab mafodotin will be triggered by grade 2 or worse events of ocular exam findings, or decrease in BCVA on day of dosing.

- a) Mild superficial keratopathy is mild superficial punctate keratopathy (documented worsening from baseline), with or without symptoms.

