#### 5.2.4 Corneal Supportive Care Guidelines for Belantamab Mafodotin

Corneal events, which commonly manifest as superficial keratopathy, have been observed with antibody drug conjugates, including those conjugated to MMAF. As there is no single term which adequately captures these events, the term "corneal events" includes preferred terms describing corneal events reported with belantamab mafodotin, such as superficial punctate keratopathy, microcyst-like changes, subepithelial haze, corneal erosions and corneal ulcers.

Sites are required to establish a close collaboration with a qualified eye care specialist who will be responsible for assessing participants and managing those who develop corneal examination findings in close communication with the MCW PI (cc: MCW Multisite Team email).

Participants will be assessed by a qualified eye care specialist at screening/baseline and then prior to every dosing of belantamab mafodotin, and 70-day safety visit (assessment window of up to five days prior to dosing, but all effort should be made to schedule as close to belantamab mafodotin dosing as possible).

• If a participant subsequently develops vision changes or other ocular symptoms, the participant should be evaluated by a qualified eye care specialist.

2. Counting fingers at 2 feet.

3. Holladay JT. Visual acuity measurements. J Cataract Refract Surg. 2004; 30:287-290

4. Non-snellen acuity of 'light perception' or 'no light perception' do not have corresponding values.

- In case of persistent ophthalmologic exam findings, newly developed ocular symptoms or vision changes, the participants will have further ophthalmologic exams, at least every cycle until resolution (to grade 1 or baseline) or more frequently as clinically indicated by a qualified eye care specialist.
- Participants who have corneal signs per the Keratopathy Visual Acuity (KVA) scale for treatmentrelated corneal toxicities present at the end-of-study treatment will continue to be followed every three months for up to 12 months, or until full resolution of findings, which is defined as a return to participant's baseline, or until deemed clinically stable by a qualified eye care specialist, whichever comes first.

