#### **Secondary outcomes**

Time-to-event outcomes, such duration of response, time to progression/relapse, progression-free survival, and overall survival will be described using the Kaplan-Meier estimator. Left truncation at the start of study treatment will be used. Best objective response on the trial and negative MRD prevalence at specific timepoints will be summarized as counts with percentages. Quality of life scores will be summarized at each timepoint with descriptive statistics and analyzed using mixed effect models with a random subject intercept.

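### OSDI is tied to dosing days and the 70-day visit, with none during a corneal hold, so by-cycle summaries are likely to under-record eye symptoms when corneal toxicity is at its worst

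*Combined protocol and SAP*

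**What the plan says.** **OSDI schedule.** Footnote 17 of the study calendar reads "Collect at cycle 1 day 1 (prior to treatment), every cycle day 1, and 70-day safety visit". The calendar grid agrees: PRO questionnaires are marked at day 1 of cycles 1 to 12 and at the 70-day visit, and nowhere else. The same footnote puts PROs ahead of the other procedures at a visit, blood draws excepted.

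**Day 1 is the dosing day.** In the Protocol Summary, "belantamab mafodotin will be administered at a dose of 1.9 mg/kg IV on day 1 of each cycle".

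**Corneal hold.** For KVA grade 2, Table 4 in section 5.2.3 says "Withhold belantamab mafodotin until improvement in both corneal examination findings and changes in BCVA to grade 1 or better and resume at current dose". Grade 3 has the same recovery condition, as does grade 4 if treatment is to resume.

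**Delayed cycles.** Footnote 9 speaks of resuming a treatment cycle, with a 16-week limit counted from the previous day 1. Beyond that, treatment may be permanently discontinued.

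**Visits during a hold.** Section 5.2.4 requires eye exams at least every cycle while findings persist. Section 3.1 keeps disease evaluations at least every 56 days (± seven) for all subjects.

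**Analysis.** Section 8.2.5, secondary outcomes: "Quality of life scores will be summarized at each timepoint with descriptive statistics and analyzed using mixed effect models with a random subject intercept". It gives no rule for delayed cycles and no link to KVA grade.

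**The concern.** The same eye findings that OSDI is meant to describe also decide when a dose is given. If cycle day 1 moves with the dose, a held patient's next OSDI is completed once the cornea is back to grade 1 or better and is filed as the next cycle's score. The record then looks complete while the toxic interval goes unsampled, and a summary by cycle leans toward fewer symptoms.

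Corneal events are on the protocol's list of adverse events of special interest, and quality of life is a secondary endpoint. At stake is whether the trial can describe how patients experience the drug's corneal effects. Scores not collected during a hold cannot be recovered later.

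**Working it through.** The documents give no figure for this point, so the check is a comparison of visits, a timeline and an illustration.

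**1. Which visits carry an OSDI**

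| Visit | Continues during a corneal hold? | OSDI scheduled? |
|---|---|---|
| Cycle day 1 (footnote 17) | Not stated; footnote 9 suggests it moves | Yes |
| Eye exam for persistent findings (5.2.4) | Yes, at least every cycle | No |
| Disease evaluation (3.1) | Yes, at least every 56 days | No |
| 70-day safety visit (footnotes 10 and 17) | Only if treatment has ended | Yes |

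The eye exam may be up to five days before dosing (footnote 2), so a hold can be decided before the day 1 visit takes place.

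**2. Timeline, with C1D1 as day 0.** Section 1.4 cites a median onset of the first keratopathy finding of 37 days and a median recovery of 86.5 days (range 8–358), from an earlier trial at 2.5 mg/kg every three weeks. Assume for illustration that they apply here.
- The toxic period runs from day 37 to day 37 + 86.5 = 123.5. The planned C2D1, day 56, lies inside it.
- If OSDI is completed at the planned C2D1 visit, the episode is sampled once, 56 − 37 = 19 days after onset.
- If an eye exam up to five days earlier leads to a hold and C2D1 moves, the first OSDI on resuming falls at day 123.5 and the episode is missed. That is past the 16-week limit (day 112), so treatment may instead have stopped.
- The 70-day window covers days 67–73 after the last dose. It closes 112 − 73 = 39 days before the 16-week limit, so a patient held to that limit may pass it before discontinuation is decided.
- With recovery in 8 days (days 37–45), the episode falls between planned visits whether or not there is a hold. With recovery in 358 days (days 37–395), days 56 and 70 both fall inside.
- OSDI asks about the last week. Its recall covers 7/56 = 12.5% of a normal interval and 7/112 = 6.25% of an interval stretched to the limit.

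**3. Illustrative size.** Simulation over 336 days (six 56-day timepoints). All inputs are assumptions:
- chance of a corneal hold per cycle of 3%, 6% or 12%, so the share of patients ever held is 1 − 0.97^6 = 17% to 1 − 0.88^6 = 54%;
- onset uniform over the 28 days before the exam;
- lognormal recovery (log-scale SD 0.75) with median 28, 56 or 86.5 days;
- no cap at 16 weeks;
- a 20-point OSDI difference between toxic and recovered periods.

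Understatement of mean OSDI = (share of timepoints in a toxic period) × (fraction of those missed) × 20.

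| | 3% per cycle, median 28 days | 12% per cycle, median 86.5 days |
|---|---|---|
| Share of timepoints in a toxic period | 0.03 | 0.20 |
| Missed if OSDI is done at the hold-decision visit | about 12% | about 46–47% |
| Understatement in that case | 0.03 × 0.12 × 20 ≈ 0.1 | 0.20 × 0.46 × 20 ≈ 1.8 |
| Understatement if that visit yields no OSDI (nearly all missed) | 0.03 × 20 = 0.6 | 0.20 × 20 = 4.0 |

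The understatement is proportional to the assumed difference: 10 points halves it and 30 points raises it by half.

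**The case against.** **The moving of day 1 is an inference.** No text says that a corneal hold shifts it. The afebrile neutropenia row of Table 3a describes a day 1 on which the dose is withheld, with dosing resumed on day 1 of a later cycle. This stands. A reader might infer that a post-baseline day 1 can occur only at KVA grade 1 or better; the documents do not go that far. They leave the matter open, and sites could handle it differently.

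**Some toxicity will be captured.** PROs come first at the visit, and the note under Table 5 says dose reductions are "triggered by grade 2 or worse events of ocular exam findings, or decrease in BCVA on day of dosing", so OSDI may well be completed at the visit where a hold is decided. The 70-day visit can capture patients who stop for corneal events. Grade 1 findings are sampled because dosing continues. All of this stands. It rules out saying that OSDI is collected only on cycle day 1, or that nearly all of the toxicity signal is lost regardless of how the hold visit is handled. But the order of procedures within a visit does not create a visit during the hold.

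**The borrowed figures may be too high.** Dose delay for keratopathy in 45 of 95 patients (47%) and the 86.5-day recovery come from a higher dose given every three weeks, and section 1.3 expects less ocular toxicity with eight-weekly dosing. Recovery there meant resolution or return to baseline, whereas a hold here ends at grade 1. They may overstate hold frequency and length.

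**The mixed model is not itself at fault.** One might say that it cannot recover missing scores. If day 1 moves, the score is delayed rather than missing. The weakness is when the score is taken and how it is labelled.

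**Safety oversight does not rest on OSDI.** Corneal events are graded on the KVA scale, changes in adverse event grade are recorded, and grade 4 corneal events have a monitoring boundary (Table 6). No stated dosing, stopping or efficacy decision uses OSDI.

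**Conclusion.** The point holds as a gap in data collection. OSDI is attached to day 1 and the 70-day visit, and to none of the visits that continue during a corneal hold. If day 1 moves with the dose, by-cycle summaries will under-record ocular symptoms at their worst. If it does not, the protocol needs to say so.

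Under the stated assumptions 3–20% of 56-day timepoints are in a toxic period. About 12–47% of these are missed when OSDI is completed at the hold-decision visit (mean understated by about 0.1–1.8 points), and nearly all when it is not (about 0.6–4.0 points). These sizes depend on a 20-point difference with no source in the documents, so they show scale and are not estimates for this trial. The conclusion that no OSDI is scheduled during a hold depends on none of them.

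The change is worth making because it is cheap and the loss cannot be repaired later. The finding does not touch the primary endpoint or the toxicity monitoring rules.

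**What to change.** - **Footnote 17:** collect OSDI at planned 56-day dates counted from C1D1 (± seven days), whether or not a dose is given, and at each protocol-required eye exam during a corneal hold.
- **Footnote 9 and Table 3a:** reconcile the wording so that it is clear whether cycle day 1 moves when a dose is held, and how a visit with a withheld dose is labelled in the data.
- **Section 8.2.5:** analyse OSDI by time since C1D1 and tabulate it against the KVA grade of the same date.

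The cost is a 12-item form at visits the protocol already requires, plus a few lines of text. Held patients have slightly more questionnaire burden. No dosing or hold rule changes.

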#### LIST OF ABBREVIATIONS

ADPR adenosine diphosphate-ribose

AE adverse event

ALL acute lymphoblastic leukemia

ALT alanine aminotransferase

AML acute myelogenous leukemia

ANC absolute neutrophil count

ASCO American Society of Clinical Oncology

ASCT autologous stem-cell transplantation

AST aspartate aminotransferase

BM bone marrow

BMA bone marrow aspiration

BSA body surface area

BUN blood urea nitrogen

CBC complete blood cell (count)
CFR Code of Federal Regulations

CL clearance, IV dosing

CLL chronic lymphocytic leukemia

CR complete response

CRC clinical research coordinator

CRF case report form

CRi complete remission with incomplete blood count recovery

CRM continual reassessment method

CRP C-reactive protein
CSF cerebral spinal fluid

CT computerized tomography

CTCAE Common Terminology Criteria for Adverse Events

CYP cytochrome P450

DLT dose-limiting toxicity
DNA deoxyribonucleic acid

DSMC Data and Safety Monitoring Committee

DSMP data and safety monitoring plan

ECG electrocardiogram

ECOG Eastern Cooperative Oncology Group

eCRF electronic case report form

**EDC** electronic data capture end of study (visit) EOS

**EOT** end of treatment (visit)

**FDA** United States Food and Drug Administration

**GCP** good clinical practice

G-CSF granulocyte colony stimulating factor

GI gastrointestinal

GLP good laboratory practices **GMP** good manufacturing practice

Hb hemoglobin HCT hematocrit

**HDT** high-dose therapy

HGB hemoglobin

HIV human immunodeficiency virus

ΙB investigator's brochure **ICF** informed consent form

**ICH** International Conference on Harmonization **IMWG** International Myeloma Working Group

**IEC** independent ethics committee

ΙP investigational product

**IRB** Institutional Review Board infusion-related reaction **IRR** 

ITT intent to treat

intravenous; intravenously IV

kDa kilodalton

**KPS** Karnofsky Performance Status

LDH lactate dehydrogenase LFT liver function test(s)

**MCWCC** Medical College of Wisconsin Cancer Center MedDRA Medical Dictionary for Regulatory Activities **MIDD** monoclonal immunoglobulin deposition disease

MM multiple myeloma

**MMBD** multiple myeloma bone disease MRI magnetic resonance imaging **MRD** minimal residual disease **MRU** medical resource utilization

Short Title: MCW EMBRACE TRIAL 17 Version No.: 3 MTD maximum-tolerated dose

NDMM newly diagnosed multiple myeloma

NCI National Cancer Institute
NHL non-Hodgkin lymphoma
ORR overall response rate

PBMC peripheral blood mononuclear cell

PCR polymerase chain reaction

PD disease progression

PFS progression-free survival

Pgp P-glycoprotein PK pharmacokinetics

PO per os; by mouth (orally)

PR partial response

PRO subject-reported outcome

PIM proto-oncogene serine/threonine-protein kinase

QTc rate-corrected QT interval (millisec) of electrocardiograph

RBC red blood cell (count)
RI renal impairment

RRMM relapsed and/or refractory multiple myeloma

SAE serious adverse event

SC subcutaneous

sCR stringent complete response

SD stable disease

SD standard deviation

sFLC serum-free light chains

sIRB single Institutional Review Board SmPC summary of product characteristics

SPEP serum M-protein immunoelectrophoresis

SRC Scientific Review Committee

SQ subcutaneous

 $t_{1/2}$  terminal disposition half-life

TEAE treatment emergent adverse events

 $T_{max}$  single-dose time to reach maximum (peak) concentration

TTP time to progression

ULN upper limit of the normal range

UP unanticipated problem

UPEP urine M-protein immune-electrophoresis

UPIRSO unanticipated problems involving risks to subjects or others

US United States

VGPR very good partial response
WBC white blood cell (count)
WBLD whole-body low dose

WHO World Health Organization

Short Title: MCW EMBRACE TRIAL

19

Version No.: 3

Version Date: 12/29/2022

#### 1 BACKGROUND

#### 1.1 Multiple Myeloma

Multiple myeloma (MM) is a malignant plasma cell disease that is characterized by clonal proliferation of plasma cells in the bone marrow and the production of excessive amounts of a monoclonal immunoglobulin (usually of the IgG or IgA type or free urinary light chain [paraprotein, M-protein or M-component]).(1) It is a disease predominantly associated with advancing age with more than 80% of patients aged 60 years or older.(2) Patients with MM may experience bone pain, bone fractures, fatigue, anemia, infections, hypercalcemia, and kidney problems.(3) The disease course for MM varies with the aggressiveness of the disease and related prognostic factors. Median survival is approximately three years; however, some patients can live longer than 10 years.(4) Treatment options and survival are based on the patient's age, fitness, and disease status.

Patients under the age of approximately 65, presenting with symptomatic active disease in good physical health will generally receive initial therapy with autologous stem cell transplantation (ASCT). To achieve cytoreduction of the disease before collecting stem cells, induction chemotherapy is administered. Induction treatment regimens include alkylating agents, dexamethasone alone, thalidomide plus dexamethasone, and vincristine, Adriamycin® (doxorubicin), and dexamethasone (VAD; or modifications to this regimen); however, the latter two regimens are associated with higher toxicity. (3, 4) Newer treatments with Velcade® (bortezomib) alone, bortezomib combinations, and Revlimid® (lenalidomide) plus dexamethasone show some promise as induction therapy, and these agents demonstrate higher response rates and lower toxicity.(3, 4)

The current aim of MM therapy is to control disease as effectively as possible, to maximize quality of life and to prolong survival. Treatments for relapsed and/or refractory disease are often referred to as salvage therapy. The initial chemotherapy regimen (e.g., melphalan plus prednisone or VAD) can be reinstituted for relapsed/refractory disease if the disease relapsed more than six months after the last therapy ended. The patients for whom stem cells were cryopreserved early in the disease course, and who are transplant candidates, can benefit from ASCT as salvage therapy.(3, 4) Subsequent treatment decisions are based on whether the patient experiences an indolent or aggressive relapse. Patients with relapsed disease may continue taking one drug or treatment regimen as maintenance therapy until relapse or toxicity. In general, MM patients will receive an average of four to eight different regimens during their lifespan utilizing agents such as proteasome inhibitors (e.g., bortezomib and carfilzomib) and immune modulatory agents (e.g., lenalidomide and pomalidomide). However, once a patient becomes refractory to those agents, survival is limited, and newer treatment options are needed to treat patients after they have failed stem cell transplant, chemotherapy, proteasome inhibitors, and immunomodulatory imide agents (IMiDs®). Despite the dramatic improvement in patient outcomes with newer therapies, MM remains an incurable disease. Thus, the treatment of patients who have received at least three different lines of therapy including a proteasome inhibitor and an immunomodulatory agent or who are double refractory to a proteasome inhibitor and an IMiD® remains an unmet medical need.

